 - AHP follows guidelines for cleaning shared work areas in the UCSF Protocol for Working Onsite. Using disinfecting wipes or other EPA-approved disinfectants, staff clean frequently touched surfaces in the lobby, other common areas, and spaces accessed by clients. Caddies containing cleaning supplies and instructions are provided in each area that requires daily disinfection. Rooms in which clients are seen for services are left vacant for at least 30 minutes after cleaning and before they can be used again for another client

appointment. A janitorial service provides additional daily cleaning of kitchen, lab, and restrooms.

- AHP continuously assesses and revises COVID prevention policies and procedures based on direction from UCSF. The Medical Director and Operations Manager shares responsibility for reviewing new guidance, revising workplans accordingly, and notifies staff, clients, and other visitors as well as other UCSF entities (e.g., Emergency Operations Center, Environmental Health & Safety, Facilities) as needed.

2. In the event that in-person contact due to the SARS CoV-2 pandemic is restricted by UCSF, SFDPH, or any other entity, the following modifications will be made to conduct visits remotely:

Remote Pre-Screening: Procedures will take place exclusively by telephone or using an approved teleconference platform (Zoom, Facebook Messenger video chat, Apple FaceTime, Google G Suite Hangouts video or Skype for business).

Remote Eligibility Visit: RAs send the verbal ICF to the partners by email, surface mail, or DocuSign and schedule a time to review the ICF with each. Using their copy, each partner will follow along during the informed consent discussion which will occur by phone or on an approved videoconferencing platform (Zoom, Facebook Messenger video chat, Apple FaceTime, Google G Suite Hangouts video or Skype for business). RAs verify HIV status of each partner to determine couple eligibility by:

- a. Participant can text a photo of a recent (last 30 days) HIV Letter of Diagnosis, HIV medication bottle, or medication prescription if HIV-positive;
- b. Participant may text a photo of a recent (last 30 days) PrEP medication bottle or prescription if HIV-negative and on PrEP;
- c. HIV-positive status can be verified for formerly participants of the Healthy Divas study for HIV-positive trans women;
- d. Participants self-administer an OraQuick HIV antibody test that is mailed to them with instructions, and text back a photo of the test result (**See T2 Participant OraQuick Instructions**);
- e. Participants self-administer an OraQuick HIV antibody test that is mailed to them while a trained HIV Pre/Post-test counselor provides step-by-step guidance by phone or using an approved video-conference platform.
- f. RA enters HIV status of partners into REDCap, which informs the RA if the couple can enroll based on their HIV status and responses to eligibility questions. Study enrollment requires participation of each partner, as a couple. If both agree, an Enrollment Visit is scheduled. Each partner is emailed a Resource List. Visit incentives are provided in the form of an Amazon gift code emailed to participant, cash mailed to a secure address with the understanding that if lost by USPO it cannot be replaced, or sent via CashAp.

Remote Enrollment Visit:

1. Each partner is sent the study ICF and a Release of Information for their care provider if HIV-positive, via email, surface mail, or DocuSign. After reviewing the ICF and answering questions, RAs help participant to sign and return the ICF and ROI. If P1 and/or P2 are unable to use DocuSign, two paper copies of the ICF (and appropriate ROI form) are mailed along with a stamped, self-addressed envelope. When received, RA sets up a videoconference or phone call to review ICF (and ROI) and answer questions. Participants sign one copy to return in the stamped-self-addressed envelope and retain the second copy.

2. RAs collect Contact Locator Information from each partner on the phone or via an approved videoconference platform (Zoom, Facebook Messenger video chat, Apple FaceTime, Google G Suite Hangouts video or Skype for business).

3. RAs complete REDCap Enrollment Visit Forms and conduct Baseline Survey separately with P1 & P2 by phone, zoom, or on an approved video-conferencing platform.

4. RAs determine the correct labs to collect from P1 and P2.

- If participant is **HIV-negative and not taking PrEP**, no labs are required.
- If participant is **HIV-positive**, the participant is asked to go to a **QUEST Patient Service Center** to have their blood drawn for HIV viral load test processing. See **Attachment T2 Participant Instructions for Quest Blood Collection**.
- If the participant cannot or will not agree to any of these methods, they may send us a recent (last 30 days) HIV viral load lab result OR using a ROI, we will request an HIV viral load result from within the last 30 days from the medical provider.

5. REDCap provides the RAs with the couples' randomization arm and the RAs inform them of the assignment.

6. Couples assigned to the control condition are emailed the HIV-risk reduction video set to watch, and RAs schedule the 3, 6, 9, and 12-month follow-up visits for the couple.
7. Couples assigned to the intervention arm are contacted by a Health Counselor, who schedules and conducts the four weekly intervention sessions on an approved videoconference platform, ensuring the couple has adequate privacy.
8. Each partner is emailed a Resource List. Visit incentives are provided in the form of an Amazon gift code emailed to participant, cash mailed to a secure address with the understanding that if lost by USPO it cannot be replaced, or sent via CashAp.

Remote Quarterly Follow-up visits

1. RAs collect Contact Locator Information from each partner on the phone or via an approved videoconference platform (Zoom, Facebook Messenger video chat, Apple FaceTime, Google G Suite Hangouts video or Skype for business).
2. Follow-up surveys are interviewer-administered on the phone or an approved teleconference platform.
3. RAs determine the correct labs to collect from P1 and P2.
 - If participant is **HIV-negative and not taking PrEP**, no labs are required.
 - If participant is **HIV-positive**, the participant is asked to go to a **QUEST Patient Service Center** to have their blood drawn for HIV viral load test processing. See **Attachment T2 Participant Instructions for Quest Blood Collection**.
 - If the participant cannot or will not agree to any of these methods, they may send us a recent (last 30 days) HIV viral load lab result OR using a ROI, we will request an HIV viral load result from within the last 30 days from the medical provider.
4. Each partner is emailed a Resource List. Visit incentives are provided in the form of an Amazon gift code emailed to participant, cash mailed to a secure address with the understanding that if lost by USPO it cannot be replaced, or sent via CashAp.

8.11 INSTRUMENTS: List all questionnaires, surveys, interview, or focus group guides that will be used for this study:

If the instruments are not complete or not available because they will be developed as part of this study, describe the basic content or include an outline and submit the final versions to the IRB with a modification for approval prior to use.

Assessments focus on: (1) predisposing factors related to our mechanisms and the CR-HIV outcome; (3) measures of feasibility/acceptability; (4) primary and secondary outcomes; (5) theory-based mechanisms of action.

1. Predisposing Factors. Stigma, oppression, and relationship functioning are extra-individual predisposing factors which may influence our hypothesized mechanisms of change and CR-HIV. Participants will complete measures of relationship functioning, which include the Dyadic Adjustment scale, Commitment scale, and the Power and Attitudes in Relationships scale. We will assess everyday experiences of transgender discrimination, including discrimination experienced by male partners due to being in a relationship with a TW, as well as our validated measure of relationship stigma. We will also assess upstream structural factors that may be associated with CR-HIV (e.g., poverty, employment status).
2. Mechanism of Change. Participants will complete the Couples Efficacy to Reduce HIV Threat

scale which assesses each partner's confidence in their ability to engage in joint effort, communication, and planning and decision making together to reduce HIV. Participants will complete the Communication Patterns Questionnaire, as well as an indicator of Joint problem-solving skills, which will be assessed with the adherence problem solving / readiness scale. We will use the Dyadic Coping Inventory which assesses the extent to which couples work together, engage in mutual decision making, and engage in open communication to alleviate a stressor (e.g., minority stress and social oppression).

3. Feasibility and Acceptability of Intervention. In regards to acceptability, participants will complete the Client Satisfaction Survey at their 3-month assessment, which is an 8-item measure assessing satisfaction with the intervention. Additionally, we will track session attendance.

4. CR-HIV (primary outcome) is a couple-level binary indicator of any HIV risk (e.g., yes=1 vs. no=0), which is an algorithm based on whether one or both partners report condomless anal or vaginal sex with a HIV serodiscordant or status-unknown primary or other partner in the past 3 months. Couples are coded as 0 if neither partner reports condomless anal or vaginal sex. If one or both partners in the dyad report condomless sex with a serodiscordant or status-unknown primary or other partner, then the couple is coded as 1 if (i) the HIV-negative participant is not adherent to PrEP and/or (ii) the HIV-positive participant is not virally suppressed. Sexual risk behavior will be measured using the assessment that we have used in our previous studies to explore the number of occasions of different sexual acts (vaginal, anal; receptive, insertive) with three different types of partners (primary partner, casual partner, paying partner), use of condoms during the past 3 months, and knowledge about partners' HIV status. Assessments ascertain sexual behaviors with non-trans male, non-trans female, and transgender partners, and will be asked at each follow-up. At-risk sex will be defined as any vaginal or anal intercourse without condoms that occurs with a person of known positive or unknown serostatus during the follow-up period. Of the participants who report condomless sex with a serodiscordant or unknown serostatus partner, we will attempt to assess PrEP use using dried blood spot (DBS) procedures for biological measurement of adherence from tenofovir diphosphate concentrations in blood plasma. We will use dosing categories for quantification similar to those used in past drug-level studies of PrEP adherence, allowing us to estimate the number of tablets participant are taking per week (e.g., 700-1249 fmol for 4-6x per week and > 1250 for daily dosing). HIV-positive participants will have their blood drawn at each follow-up visit to determine viral suppression. Viral suppression is indicated by an undetectable HIV-1 level on the COBAS® AmpliPrep/COBAS® TaqMan® HIV test kit (Roche Molecular Systems, Inc.), which has a threshold for undetectability = < 20 copies/mL and is conducted at each follow-up assessment visit. Our secondary outcomes include self-report HIV and STI testing over the 12 months of follow-up.

5. Theory-based mechanisms of action. Covariates will include sociodemographic variables such as age, education and income level, employment, race/ethnicity, living situation, which have been previously found to be structural drivers of HIV risk. While the intervention does not target mental health or substance use, we will assess depressive symptoms using the Center for Epidemiologic Studies Depression Scale (CES-D), and anxiety symptoms will be measured with the Beck Anxiety Inventory. We will also assess alcohol use and other drugs with the AUDIT as well as the Alcohol, Smoking, and Substance Involvement Test (ASSIST) given their associations with HIV outcomes. We will also assess history/current health care engagement (i.e., HIV prevention, primary care, mental health).

Attach any unpublished instruments in the 'Other Study Documents' section of the Initial Review Submission Packet form after completing the study application. Published instruments should NOT be attached.

8.12 * BIOSPECIMEN COLLECTION: Are you drawing any blood or collecting other biosamples (e.g. tissue, buccal swabs, urine, saliva, hair, etc.) for analysis under this protocol and/or storage for future research: (REQUIRED)

Yes No

* Could this study generate genetic data that may be broadly shared (e.g., submitted to NIH in compliance with **Genomic Data Sharing (GDS)/Genome-Wide Association Studies (GWAS)** requirements): (REQUIRED)

Yes No

Please check the Resource Sharing Plan section of your funding notice. You will not be able to share the data as required by your

funding agency if the consent form doesn't include the required language.

8.13 STATISTICAL METHODS: Briefly summarize the methods and types of analyses that will be performed:

Preliminary analyses and missing data. Frequency tables for all variables and measures of central tendency and variability for continuous variables will characterize the sample and will be stratified by study arm to check for imbalances. If the intervention and control groups differ significantly at baseline on one or more covariates, we will use methods based on the Rubin causal model (e.g., propensity scores, double-robust estimation) to obtain the desired marginal effect estimates under the counterfactual assumption of balanced groups.⁸¹⁻⁸⁵ We will address incomplete data with multiple imputation (MI)⁸⁶ because MI makes the relatively mild assumption that incomplete data arise from a conditionally missing-at-random (MAR) mechanism.⁸⁷

Auxiliary variables will be included to help meet the MAR assumption;^{88, 89} sensitivity analyses will be conducted with weighted MI to assess the MAR assumption's robustness⁹⁰ using SAS⁹¹ and Mplus.

Primary analyses to address Primary Specific Aim 1. If the CHIP intervention is successful, a lower proportion of intervention participants will engage in CR-HIV relative to control group participants following intervention exposure. Therefore, to address Specific Aim 1 we hypothesize that the odds of CR-HIV will be lower for CHIP participants than for control participants (Hypothesis 1). Our primary interest is to estimate the marginal or population-average effects of CHIP exposure on CR-HIV rather than the effect for a hypothetical average subject or couple.⁹² Moreover, within-subject and within-couple CR-HIV correlations are nuisance parameters rather than quantities of interest to be modeled explicitly. Finally, the statistical literature indicates the superior performance of generalized estimating equations (GEE) relative to generalized linear mixed models (GLMMs) for the analysis of dyadic data with categorical outcomes such as CR-HIV.⁹³ Accordingly, we will use GEE for the proposed primary analysis to test Hypothesis 1 by a planned time-averaged comparison of post-baseline measurements of CR-HIV from the intervention group with the post-baseline measures of CRHIV from the control group. Alpha (α) will be set at .05 for this planned comparison. Any additional post-hoc comparisons (e.g., paired comparisons of groups at each time point) will maintain nominal alpha of .05 through the use of simulation-based stepdown multiple comparison methods.⁹⁴ The alternating logistic regression (ALR) approach implemented in SAS PROC GENMOD will be used to address the 3-level clustering of observations within participants and participants within dyads. Though GEE estimates are consistent even if the correlation structure is misspecified, GEE's statistical efficiency improves as the working correlation structure more closely approximates the actual correlation structure;⁹⁵ therefore, various correlation structures suitable for the study's design will be considered (e.g., exchangeable; nested-1).⁹⁶ The QIC statistic will be used to select the final correlation structure.⁹⁷ Couple serostatus will be included as a covariate as required by the stratified randomized design.⁹⁸ Additional relevant covariates such as relationship length, as well as intersectionality criteria and structural drivers (e.g., age, race/ethnicity, poverty, unemployment) will be included if they improve QIC. We will use Robust Huber-White "sandwich" standard errors to obtain correct inferences even if the chosen correlation structure remains slightly misspecified.

Secondary analyses to address Secondary Specific Aims 1 and 2: Exploring mediation and moderation. To explore the effect of CHIP on hypothesized mechanisms of change, secondary analyses will explore whether participants assigned to CHIP report higher mean scores on theory-based constructs such as couple selfefficacy, communication and joint problem-solving strategies, and dyadic coping with gender minority stressors following the intervention. These analyses will also investigate whether these constructs at 3, 6 and 9 months mediate the relationship between intervention group assignment and CR-HIV at 6, 9 and 12 months, respectively, and whether couple HIV-serostatus and (in line with NIH guidelines to consider sex as a biological variable) whether gender moderate these associations. Mediation and moderation will be assessed using the causal inference-based approach of Valeri and VanderWeele, which yields optimal estimates of indirect effects in the presence of moderators and non-continuous outcomes and mediators.⁹⁹ Mplus will be used to fit causal mediation-moderation models because it adjusts standard errors for clustering of participants within couples.

Secondary analyses to address moderation and subgroup differences in intersectional variables. As noted above in C.1 Preliminary Studies, the intervention is designed to be equally efficacious across intersectional subgroups of participants, so we do not anticipate differential intervention effects by subgroup. However, we will conduct additional exploratory sensitivity analyses to evaluate the moderating effects of age, HIV status, race/ethnicity, poverty, and unemployment to explore whether these intersectionality criteria and structural drivers enhance or dampen the intervention's effects on CR-HIV and the theory-based mediators listed above. Where cell sizes permit, subgroup analyses will be performed, stratifying on race/ethnicity, age, and poverty. While our study is not formally powered to examine subgroup differences and it would be

infeasible to recruit sufficiently large numbers of participants in each intersectional category to formally test for differences, these analyses may illuminate trends in group differences, which can inform future studies of specific subpopulations if trends are detected. Moderation and subgroup analyses will be performed using the same GEE and causal inference approaches described above to test for moderation and moderated mediation, respectively.

Secondary exploratory dyadic analyses. Intact dyads enable analyses that explore how predisposing factors, such as relationship functioning and gender minority stressors affect behavior change in partnerships. We will extend the analyses described above to include actor and partner effects for covariates and mediators. Actor effects describe the influence that one's standing on independent or mediating variables (e.g., the trans woman's communication) has on one's own dependent variables (e.g., self CR-HIV) whereas partner effects describe the influence that one's standing on independent variables has on the dependent variables of one's partner (e.g., the trans woman's effect on her partner's CR-HIV). This technique illuminates the effects that partners in intimate relationships can have on both their own and their partner's behaviors. Actor and partner effects can be evaluated in models with either continuous¹⁰¹ (e.g., problem solving) or categorical dependent variables (e.g., CR-HIV).¹⁰⁰ A closely related approach uses sums and differences of continuous covariates and mediators to quantify within-couple and between-couple effects. For continuous dependent variables, within-couple hypotheses will be tested with a GEE model in which couple-level difference scores on the outcome variable (e.g., communication) will be regressed onto both the couple-level difference and sum scores for the predictor variable (e.g., self-efficacy).¹⁰² Computing sums and differences for categorical outcomes is not feasible, but it is still possible to investigate the effects of sums and differences of individuals' continuous covariates and mediators on individual-level categorical responses (e.g., CR-HIV) to tease apart the separate influences of between-couple and within-couple effects of mediators on individuals' categorical outcomes.

8.14 REFERENCES: List only the 5-10 most relevant references (a separate bibliography can be attached for reference purposes if this study involves novel approaches, agents, or an emerging technology that the IRB may not be familiar with):

2. [name] D, Nemoto T, Iwamoto M, et al. Unprotected sexual behavior and HIV risk in the context of primary partnerships for transgender women. *AIDS Behav.* 2011;15(3):674-682. PMC3049202

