8.0 Research Plan and Procedures

8.1 HYPOTHESIS: Describe the hypothesis or what the study hopes to prove:

We hypothesize that couples in the intervention condition will have lower Composite Risk for HIV (CR-HIV) at 12-month follow-up compared to couples in the control condition.

8.2 AIMS: List the specific aims:

The primary specific aim is to:

1. Evaluate the efficacy of the T2 couples HIV counseling intervention on Composite Risk for HIV (CR-HIV) compared to an enhanced standard of care (SOC) control condition.

The secondary aims are to:

1. Assess the effects of the T2 couples HIV counseling intervention on theory-based mediators (i.e. couples' self-efficacy, communication and joint problem-solving skills, coping with gender-based minority stress and social oppression).
2. Explore partner gender, couple HIV status (seroconcordant negative/seroconcordant positive /serodiscordant) as moderators of the effect of the intervention on CR-HIV.

8.3 DESIGN: Briefly describe the study design (e.g., observational, interventional, randomized, placebo-controlled, blinded, cross-over, cross-sectional, longitudinal, pharmacokinetic, etc.):

Using a two-arm randomized controlled trial (RCT) design, we will examine intervention effects on Composite Risk for HIV (CR-HIV) at 12-month follow-up comparing couples randomized to the intervention versus an enhanced standard of care (SOC). To achieve these aims, we will recruit and randomize 54 couples (108 participants) to test a theory-based couples-focused intervention that addresses within-couple and extra-dyadic sexual risk, structural factors related to risk, routine testing for HIV and other sexual transmitted infections (STI), preexposure prophylaxis (PrEP) uptake and adherence, and antiretroviral therapy (ART) adherence (for couples in which one partner is HIV-positive).

After completing baseline surveys, couples are randomized (stratified by couple serostatus at enrollment) to the intervention or enhanced standard of care using a computerized secure and fraud-resistant procedure employed in our teams prior studies. UCF has used this method in several RCTs; our experience with over 700 participants indicates that it is successful in achieving balance across demographic, mediating, and outcome variables.

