Original Power Calculations. Originally, our sample size of 100 couples would allow us the statistical power to engage in meaningful comparisons between the two intervention arms. We assumed the 200 participants from 100 couples will be evenly assigned to the intervention arms: 50 couples in intervention and 50 couples in control. Assuming 20% attrition, data from 160 participants (80 couples) would have been available for analysis at all time points (i.e., 3-, 6-, 9, 12-month follow up). Using NCSS PASS, we conducted a series of power calculations to determine the maximum sample size requested to address the primary study aims. We computed the minimum detectable odds ratio (OR), proportion difference (pdiff), and standardized proportion difference (h) across our two study arms for the proposed time-averaged comparisons, assuming four post-baseline measurements and a wide range of base proportions for levels of risk for TW and their partners seen in the literature (i.e., 10%-50%). Since the within-subject correlation ρ for repeated measures is unknown, we varied it across a wide range from .20 to .80. Under these conditions, ORs ranged from 0.17 to 0.56, raw proportion differences ranged from 6.6% to 20.5%, and standardized proportion differences (h) ranged from .27 to .42. **Revised Power Calculations.** We repeated the power analysis approach utilized in our proposal submission. The revised power analysis again assumes $\alpha=0.05$, power=0.80, 4 post-baseline measurements, and baseline reference proportions ranging from 0.10 to 0.50. The within-subject correlation for repeated measures was allowed to vary from 0.20 to 0.80. The N of participants was varied from 100 to 200 to illustrate the potential impact of various sample size reductions on the ranges of minimum detectable effect sizes. Conventional benchmarks for effect size are $h=0.20$ for a small effect size, $h=0.50$ for a medium effect size, and $h=0.80$ for a large effect size. Assuming we reach at least 50% of our goal of recruiting 100 couples, under most circumstances we will still be able to detect a small-to-medium effect size. Even under the least advantageous combination of circumstances (recruiting only 50 couples, baseline reference proportions closer to 10%, and very high correlations between repeated measures), a medium-to-large effect size is still detectable.

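### The stated hypothesis is about month 12, but the primary test and its power are for the average over months 3, 6, 9 and 12

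*Combined protocol and SAP*

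**What the plan says.** **Stated effect.** Section 8.1 reads "We hypothesize that couples in the intervention condition will have lower Composite Risk for HIV (CR-HIV) at 12-month follow-up", compared with control couples. Section 8.3 repeats it: "we will examine intervention effects on Composite Risk for HIV (CR-HIV) at 12-month follow-up comparing couples randomized to the intervention". The primary aim in 8.2 gives no time point.

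**Planned test.** Section 8.13 restates Hypothesis 1 without a time point and tests it by "a planned time-averaged comparison of post-baseline measurements of CR-HIV from the intervention group" against the same measurements from control. This is the one planned comparison, at alpha .05. For single visits the section says: "Any additional post-hoc comparisons (e.g., paired comparisons of groups at each time point) will maintain nominal alpha of .05", by stepdown methods. CR-HIV at individual visits otherwise appears only in secondary models of whether theory-based constructs "mediate the relationship between intervention group assignment and CR-HIV at 6, 9 and 12 months, respectively".

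**Power.** Section 11.3 computes detectable effects "for the proposed time-averaged comparisons, assuming four post-baseline measurements". The revised calculation, made for the reduced recruitment, says it repeats the same approach with four post-baseline measurements. Section 8.3 gives the current size as 54 couples (108 participants).

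**The concern.** The month-12 effect and the four-visit average are different quantities. Section 8.11 gives CR-HIV a three-month recall, so the month-12 value describes roughly months 9 to 12, while the average weights all four quarters. They coincide only if the effect is the same at every visit. The plan does not state this, and the pilot in section 8.5 reports 3-month outcomes only, so it says nothing about persistence.

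The risk lies in how the result is read. A significant average could be reported as confirming the 12-month hypothesis in 8.1 even if the benefit had gone by then. A non-significant average could be read as no 12-month effect when the test was not aimed there. The power in 11.3 would be cited for a claim it was not computed for.

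**Working it through.** **1. Inputs.** From section 11.3: alpha .05, power .80, four post-baseline measurements, control rates P0 of .10 to .50, within-subject correlation rho of .20 to .80, within-couple correlation .07. The design effect is 1 + (2 − 1) × .07 = 1.07. With 160 analysable participants, ESS = 160/1.07 = 149.5 (printed as 149), or 74.5 per arm.

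**2. Formula.** The document names a software module but prints neither the variance form nor the sidedness. A two-sided test on the log odds ratio with pooled variance fits:

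|ln OR| = (1.96 + .8416) × √[VF × 2 / (n × p̄ × (1 − p̄))]

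Here n is the number per arm and p̄ the mean of the two arms' rates. VF = (1 + 3 × rho)/4 for the four-visit average, and VF = 1 for one visit.

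**3. The plan's own figures.** At ESS 149:

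| | OR | Difference (points) | h |
|---|---|---|---|
| Printed in 11.3 | .17–.56 | 6.6–20.5 | .27–.42 |
| Four-visit average | .166–.556 | 6.6–20.4 | .275–.419 |
| Month 12 alone | .139–.390 | 8.5–21.9 | .396–.454 |

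The printed ranges are those of the average. One visit does not reproduce them.

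**4. Power at month 12 for the effect that the plan is powered for.** Assume a constant effect with 80% power on the average. Power at one visit is then Φ(2.8016 × √VF − 1.96), whatever the sample size. The stepdown row puts month 12 in a family of four visit tests, with test statistics correlated at rho (400,000 draws).

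| | rho .2 | rho .5 | rho .8 |
|---|---|---|---|
| VF | .400 | .625 | .850 |
| Month 12 alone, alpha .05 | .425 | .601 | .733 |
| Month 12 within stepdown family | about .28 | about .48 | about .66 |
| Ratio of detectable log odds ratio, 1/√VF | 1.58 | 1.26 | 1.08 |

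**5. Current sample size.** Assume that 20% attrition, the 1.07 design effect and participant-level counting carry over: 108 × .8 = 86.4, and 86.4/1.07 = 80.7, about 81. Like for like at P0 = .50, detectable h for the average is .39, .49 and .56 (rho .2, .5, .8), against .61 for month 12. Over the full P0 range it is .35–.56 against .48–.61. Counting couples instead (54 × .8 = 43.2), it is .44–.75 against .55–.81.

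**6. What the mismatch can produce.** This is an assumed pattern; nothing in the plan predicts it. Take control at 50% throughout and intervention at 25, 30, 38 and 50% at the four visits, a mean of 35.75%. In simulation the average is significant in about 55% of trials (rho .2) or 39% (rho .5) with 41 versus 40 units. With 22 versus 21 couples it is about 34% and 23%. The true month-12 effect is zero, and the month-12 test favours intervention only at the chance rate, about 2 to 3%.

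**The case against.** The strongest reply is that the operative plan is not ambiguous. Section 8.13 names one contrast and one alpha, and 11.3 powers that contrast. The analyst has no free choice of primary test, and type I error for it is not at risk. This stands: the fault is in the stated target, not in the validity of the test.

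A second reply is that 8.1 and 8.3 loosely mean the 12-month follow-up period. That is possible, but the document words the whole period differently elsewhere (8.3 on quarterly follow-up, 8.11 on secondary outcomes), and 8.5 uses the same construction for the pilot's single 3-month visit. If the loose meaning was intended, rewording is still what is needed.

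Third, a multiplicity-adjusted month-12 comparison is already possible under 8.13. True, but only post hoc. It is not named, and no estimate with an interval is promised.

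Fourth, on the figures. The power figures in step 4 assume a constant effect, which is the case where the two targets agree. They therefore measure the cost of making a separate month-12 claim, not harm to the planned test, and they favour keeping the average as primary. The fade is invented and shows only what is possible. At the current size the attrition and design effect are carried over, since the revised calculation prints neither. At rho .8 the gap is small (h .56 against .61 at P0 = .50). At P0 = .10 the month-12 solution is an intervention rate near 0.7%, about 0.3 expected events among 40, so the lower ends of those ranges are not reliable. The couple-count figures only show sensitivity to the unit of analysis, which is a separate question. None of this removes the mismatch.

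**Conclusion.** The concern holds. Sections 8.1 and 8.3 state a month-12 effect. Sections 8.13 and 11.3 test and power the average over four visits, and no part of the document reconciles them. The primary test can stand, but the hypothesis is wrong as written for that test.

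The firmest evidence is that the printed detectable effects match the four-visit average and not one visit. Under a constant effect, month-12 power is about 43 to 73% where the average has 80%, or about 28 to 66% inside a four-visit stepdown family. These figures rest on a normal approximation, equal correlation between visits, and a variance form inferred from its match to the printed ranges. The ranges for 54 couples also rest on carried-over attrition and design effect and are indicative only.

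**What to change.** 1. Reword 8.1 and 8.3 as the average effect on CR-HIV over months 3 to 12, to match the planned test, its alpha and its power basis.
2. In 8.13, pre-specify the month-12 contrast, from the same GEE with an arm-by-visit term, as a named secondary estimate with its confidence interval.
3. State its multiplicity status: either tested within the stepdown family already planned for per-visit comparisons, or reported as an estimate with no significance claim.
4. State that any claim of benefit at 12 months rests on that contrast alone.

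If month 12 is the intended primary target, make that contrast the alpha .05 test in 8.13 instead, and redo the power statement for one visit at 54 couples.

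The preferred route costs wording in two sections, one sentence on multiplicity, and one contrast from data already collected and an extension of the planned model. The drawback is precision. On the log-odds scale the detectable month-12 effect is about 1.08 (rho .8) to 1.58 (rho .2) times that of the average, before any change in the pooled variance, and stepdown adjustment lowers its power further.
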